#### Statistical analysis protocol

The primary outcome of the study is the sensitivity and specificity of the baseline MRI (bMRI) and the high-resolution MRI (hrMRI) studies, based on the standard of surgical findings on patients who underwent either intracranial EEG or surgical resection. Each of the sensitivity and specificity of the

two tiers of MRI studies (baseline MRI and high-resolution MRI) will be compared with use of contingency table and chi-square test.

The secondary outcomes would include the following:

- Number of cases with true positive, and false positive findings on bMRI or hrMRI; and descriptive statistics of findings in patients who had MRI but did not undergo surgery.
- Inter-observer and Intra-observer agreement for findings on bMRI or hrMRI by kappa statistics.

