## **Scientific basis**

Focal epilepsy refers to having seizures arising from a specific part of the brain. In these patients, workup in magnetic resonance imaging is often necessary as patients with structural lesions have a much higher rate of seizures, ranging from 10% to 26% at 1 year and from 29% to 48% at 5 years. However, there is also a subgroup of patients who has epilepsy not adequately controlled by anti-epileptics with unrevealing first MRI study, a dedicated MRI protocol may reveal positive lesion in 30-65% of the cases. In these patients, several tricks can be applied to increase the detection rate. First, the used of a high-resolution MRI on a high-field scanner could be helpful, which can be increased the sensitivity up to 90%. The use of 7T-MRI in further picking up subtle lesions in patients presenting with epilepsy has been investigated, further affirming the role of high resolution MRI imaging. Secondly, the use of dedicated sequences, such as T1-weighted inversion recovery sequences which allow better distinction of grey and white matter, could also reveal subtle lesions such as polymicrogyria or Type 1 focal cortical dysplasia.

Our study is therefore aimed to apply the findings to the local settings, and specifically to investigate if T1-weighted inversion recovery sequences provides additional benefit in picking up more subtle lesions in patients who had an initial first negative MRI.

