## **Study protocol**

This study will be a prospective cohort model comparing baseline MRI and high-resolution MRI in delineation of focal abnormalities accounting for epilepsy.

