### **Patient recruitment**

**Inclusion:** Consecutive patients with drug-resistant focal epilepsy fulfilling the following criteria –

1. Diagnosis of focal epilepsy with a probable site identified, as defined by concordant results from any TWO of the following:
  - Clinical seminology compatible with focal epilepsy.
  - Electroencephalopathy pointing towards a specific site for focal epilepsy.
  - Positive ictal brain scintigraphy with SPECT-CT correlation.

AND

2. Previous MRI (at least one study with protocol tailored for epilepsy) which did not reveal accountable focal lesion.

AND

3. Able to consent for MRI examination (if patient under age of 18, consent for MRI will be obtained from guardian). Patients will be provided information leaflets to read on, and written consent before taking part in this study and MRI examination.

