### **Sample size calculation**

There is no previous studies available specifically on the use of inversion recovery sequences.

Based on previous paper by deSantis et al. with use of 7T MRI the pickup rate of MRI on patients with previous negative MRI would be around 30%. We prudently estimate that as the current MRI, the pick up rate would be lower than an even-higher resolution 7T MRI and approximately at half of previous study quoted (i.e. 15%), and a 5% false negative rate on patients who actually had lesions on previous baseline MRI. With a 80% statistical power and two-tail alpha = 0.05, approximately 22 patients who needs to have both MRI done and undergone surgery. And assuming that only 1/3 of patients who had workup will undergo surgery, approximately 66 patients are required.

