#### Image interpretation

The baseline MRI of the patients will be retrospectively reviewed, while the MRI performed in this study will also be reviewed by two different radiologists. Radiologists are not blinded to the clinical history and site of clinical suspicion but are blinded to the subsequent surgical findings and outcomes.

The localization of the site of epilepsy will be pointed out according to a five-point confidence scale (1: very unlikely, 2: unlikely, 3: equivocal/ suspicious, 4: likely, 5: highly likely).

A likelihood score of 3 or above would indicate a positive imaging study.

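### All patients enter on a negative earlier MRI, so the primary 'accuracy of baseline MRI' is really second-look recovery; the primary comparison should be the paired difference, hrMRI minus re-read

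*Protocol*

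**What the plan says.** Four parts of the Protocol bear on this.

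- **Entry.** Patient recruitment requires: "Previous MRI (at least one study with protocol tailored for epilepsy) which did not reveal accountable focal lesion".
- **Design and primary outcome.** Study protocol describes the study as "comparing baseline MRI and high-resolution MRI in delineation of focal abnormalities accounting for epilepsy". Statistical analysis protocol then says: "The primary outcome of the study is the sensitivity and specificity of the baseline MRI (bMRI) and the high-resolution MRI (hrMRI) studies". The reference standard is surgical findings in patients who had intracranial EEG or resection. Sensitivity and specificity are each compared by contingency table and chi-square.
- **Source of the baseline result.** Image interpretation says: "The baseline MRI of the patients will be retrospectively reviewed". The radiologists know the history and the suspected site but not the surgical findings or outcome. On positivity: "A likelihood score of 3 or above would indicate a positive imaging study".
- **Aim and planning inputs.** Scientific basis asks whether the inversion recovery sequences give what it calls "provides additional benefit in picking up more subtle lesions in patients who had an initial first negative MRI". Sample size calculation starts from a yield of the same kind ("the pickup rate of MRI on patients with previous negative MRI would be around 30" per cent) and halves it to 15%.

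**The concern.** One of the two tests under comparison has decided who enters. Patients whose first report was positive are never enrolled, so nothing in this cohort can show how often baseline MRI finds a lesion that is there. The re-read gives a number, but only among lesions that the first report missed.

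No section says that the baseline figures are conditional in this way. A result labelled sensitivity and specificity of baseline MRI, with a test against hrMRI, would invite the conclusion that the two examinations differ in accuracy by that amount. What the data can support is narrower: what a new hrMRI adds to a careful second look after a negative report. That is the question in Scientific basis, and the primary outcome does not name it.

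**Working it through.** **1. What the selection does.** I take the baseline MRI to be the qualifying negative scan. The Protocol does not define it formally, but the retrospective review and the phrase "a 5% false negative rate on patients who actually had lesions on previous baseline MRI" in Sample size calculation both point that way. On the entry report, every patient is negative. Any positive baseline result therefore comes from the re-read.

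Among patients with a lesion, let s1 be the sensitivity of the entry report, s2 the sensitivity the re-read would have without selection, and ρ the correlation between the two reads. What this cohort estimates is

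P(re-read positive | entry negative, lesion) = [s2(1 − s1) − ρ√(s1(1 − s1)s2(1 − s2))] / (1 − s1).

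The Protocol gives none of s1, s2 or ρ. The values below are assumptions, shown as a range. With s1 = 50%, the cohort value as a fraction of s2 is:

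| ρ | s2 = 50% | s2 = 60% | s2 = 70% |
|---|---|---|---|
| 0 | 1.00 | 1.00 | 1.00 |
| 0.3 | 0.70 | 0.76 | 0.80 |
| 0.5 | 0.50 | 0.59 | 0.67 |
| 0.7 | 0.30 | 0.43 | not attainable (maximum ρ 0.655) |

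Example: s2 = 50%, ρ = 0.3 gives (0.25 − 0.3 × 0.25)/0.5 = 0.35, and 0.35/0.5 = 0.70.

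For specificity, with c1 (entry report) and c2 (re-read) defined in the same way among patients without a lesion, the cohort value is

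[c1c2 + ρ√(c1(1 − c1)c2(1 − c2))] / c1.

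A re-read specificity of 80% becomes:

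- ρ = 0.3: 84% (c1 = 90%) or 86% (c1 = 80%)
- ρ = 0.5: 87% or 90%

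Example: c1 = 90%, ρ = 0.3 gives (0.72 + 0.3 × 0.12)/0.9 = 0.84.

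The same formulas apply to hrMRI with its own correlation with the entry report. The contrast is tilted only as far as the re-read, made on the same images, repeats that report more than the new scan does.

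**2. What the planned contrast already contains.** Among D verified patients with a confirmed site, let g be the number found by hrMRI only and l the number found by the re-read only. Patients found by both cancel, so

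sensitivity(hrMRI) − sensitivity(re-read) = (g − l)/D.

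The net gain is thus already inside the planned sensitivity difference. What is missing is its definition as a within-patient quantity in initially negative patients, and a method that uses the pairing. An ordinary chi-square treats the two readings of one patient as two independent patients.

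**3. Precision of the paired form.** I use the Protocol's own 22 verified patients as the denominator (22 × 3 = 66 enrolled). Newcombe paired 95% intervals and exact McNemar p-values are:

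| Gained | Lost | Both | Net | 95% CI | p |
|---|---|---|---|---|---|
| 3 | 0 | 0 | 3/22 = +13.6% | −3.7% to 33.3% | 2 × 0.5³ = 0.25 |
| 4 | 1 | 1 | 3/22 = +13.6% | −8.8% to 35.3% | 0.375 |
| 6 | 0 | 0 | 6/22 = +27.3% | 6.8% to 48.2% | 2 × 0.5⁶ = 0.031 |

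The Protocol does not say whether its 15% refers to all verified patients or to those with a lesion. Expected hrMRI detections are 22 × 0.15 = 3.3 on the first reading. On the second, if for example 18 of the 22 have a lesion, they are 18 × 0.15 = 2.7. Either way about three are expected.

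**The case against.** The strongest reply is that little is actually lost. The planned sensitivity difference contains the net gain, true- and false-positive counts are a secondary outcome, and the initially negative population is stated openly. Sensitivity and specificity within a stated population are legitimate quantities, and no section claims accuracy in unselected epilepsy. The size of any tilt rests wholly on assumed inputs. A site-informed re-read that counts equivocal scores as positive may differ considerably from the first report. Specificity also matters, because a threshold of 3 invites overcalling.

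Most of this stands, and it limits the point. It does not remove it: the primary outcome is still named as the accuracy of a test on whose result patients were selected, the condition is not attached to it, and the stated test does not use the pairing.

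Three stronger readings may tempt a reader, and the documents support none of them.

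- *Baseline sensitivity is 0% and specificity 100% by construction.* That holds for the entry report only; Image interpretation scores a fresh re-read.
- *The comparison is invalid or rigged toward hrMRI.* It is valid for the question in Scientific basis, and the specificity tilt runs toward baseline MRI.
- *hrMRI serves as the reference standard.* It does not; surgical findings do.

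**Conclusion.** The point holds as a mismatch between the entry rule and the name given to the primary quantity. In this cohort the baseline figures are second-look recovery after a negative report, and no analysis of these patients can turn them into the accuracy of baseline MRI. hrMRI's figures carry the same condition.

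The direction follows from the selection: as far as the re-read repeats the first report more than hrMRI does, sensitivity leans toward hrMRI and specificity toward baseline MRI. The size is unknown. It is nil with reads independent given lesion status, and the figures for ρ of 0.3 to 0.7 show only what assumed correlations would do. The conclusion also assumes that the re-read scan is the qualifying one.

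This should be fixed, but it does not invalidate the study. Whether 22 follows from the stated planning inputs, and what the 5% term there means, are separate matters on which this point does not depend.

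**What to change.** In Statistical analysis protocol:

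1. Define the primary comparison as the within-patient difference, hrMRI minus baseline re-read, in initially MRI-negative patients verified by intracranial EEG or surgery. Report (a) detections at the confirmed site, as hrMRI only, re-read only, both and neither, and (b) false positives in the same four cells.
2. Give each a paired 95% CI or an exact McNemar test in place of the ordinary chi-square. Keep (b) beside (a), so that the specificity question is not demoted.
3. State that both tests' figures are conditional on a negative first report. Label the baseline figures 'second-look recovery in initially MRI-negative patients'. Do not present them, or the contrast, as the accuracy of baseline MRI.

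Patients, scans and reads do not change. The cost is that the head-to-head accuracy claim is given up and that the interval is visibly wide: 3 gained and 0 lost in 22 gives +14% (−4% to 33%), and exact McNemar needs 6 gained with none lost to reach p < 0.05. Making the paired difference primary is a design judgement, but it matches the aim that the Protocol states.

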### **MRI scanning**

Patient will be scheduled to be scanned at the Siemens Prisma 3T MRI scanner at MRI facility, the Chinese University of Hong Kong. The scanning protocol consists of the following staple sequences for evaluation of focal epilepsy:

- Axial, Coronal and Sagittal (left and Right) 2D T1-weighted inversion recovery sequences focusing on site of lesion.
- 3D FLAIR T2-weighted MRI whole brain with multi-planar reconstruction (MPR).
- 3D T1-weighted Sagittal MPRAGE (Magnetization Prepared - RApid Gradient Echo) with MPR.

The following sequences will be applied optionally depending on the site of clinical suspicion and whether dedicated mapping will be required:

- Diffuse tensor imaging of whole brain (DTI)
- Functional MRI (fMRI) for mapping of specific cortical function close to the suspected site of lesion.
- Oblique coronal T2-weighted sequences of the hippocampus if suspected hippocampal sclerosis.
- Thin-cut dedicated T2-weighted or proton-density weighted images.

Contrast injection is usually not required unless otherwise clinically needed (e.g. for scanning of additional clinical indications).

The basic sequences will take approximately 30minutes, and the optional sequences (if needed) would be variable, the whole protocol will be completed within 1 hour.

All high-resolution MRIs performed under this study will be reported by board-certified radiologist and be available on patient's electronic health records (ePR).

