### **Handling and Storage of personal data**

Images of MRI sequences with multiplanar reconstruction will be uploaded to patient's electronic patient records for clinical use, as well as purpose of surgical navigation planning by co-investigators performing operation. The research sequences will be stored in the database, while study images and reports will be available in the patient's electronic patient records.

All MRI scans will be stored in the picture archiving and communication system of Gerald Choa Neuroscience Center/ Prince of Wales Hospital. These images can be viewed on HA clinical workstations for the purpose of providing clinical care. Radiologist with training in Head and Neck or Neuroradiology will issue a formal radiology report regarding in the examinations, the report will be available on the ePR system.

The MRI data will be anonymized and encrypted before research analysis, which will also be done in HA clinical workstations. MRI scan data after anonymization will be stored in CUHK MRI data repository, with only non-identifiable patient particulars (age, sex, disease status) retained (informed consent obtained from patient prior to scanning). Use of selected images for publication purposes will be anticipated, patient particulars will be removed prior to exporting from HA clinical workstations.

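### Primary sensitivity and specificity use only surgically verified patients while clinicians can see the hrMRI report, and no correction is planned if that report affects who is verified

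*Protocol*

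**What the plan says.** The Protocol's Statistical analysis protocol section makes sensitivity and specificity of bMRI and hrMRI the primary outcome, "based on the standard of surgical findings on patients who underwent either intracranial EEG or surgical resection". Patients scanned but not operated on appear only in a secondary, descriptive summary of their findings.

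Sample size calculation asks for about 22 patients with both MRIs and surgery, and reaches 66 by "assuming that only 1/3 of patients who had workup will undergo surgery".

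The test under evaluation is open to the clinical team. MRI scanning states: "All high-resolution MRIs performed under this study will be reported by board-certified radiologist and be available on" the patient's electronic record. Handling and Storage of personal data says that a trained radiologist "will issue a formal radiology report regarding in the examinations, the report will be available on the ePR system", and of the images: "These images can be viewed on HA clinical workstations for the purpose of providing clinical care". Separately, under Image interpretation, "the MRI performed in this study will also be reviewed by two different radiologists". The blinding described there covers those radiologists, with respect to later surgical findings and outcomes. It does not cover whoever decides on intracranial EEG or resection.

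Patient recruitment sets two relevant entry conditions: "Diagnosis of focal epilepsy with a probable site identified, as defined by concordant results from any TWO of the following" (semiology, EEG, SPECT), and "Previous MRI (at least one study with protocol tailored for epilepsy) which did not reveal accountable focal lesion".

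**The concern.** This is the setting in which partial verification bias arises: the reference standard is obtained in a minority, accuracy is computed in that minority, and the index test result is known before verification is decided. At entry the clinical baseline MRI is negative in every patient, so hrMRI is the MRI result that varies between them and could bear on who goes forward.

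The Protocol does not say that hrMRI affects selection. Nor does it say that selection is independent of hrMRI, and the localising evidence required at entry offers other grounds. The concern is therefore conditional. If verification depends on hrMRI, both halves of the primary outcome are biased, in opposite directions, and the hrMRI-bMRI contrast moves too. Pairing the two MRIs within patients does not cancel this, because bMRI detections need not coincide with hrMRI detections.

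**Working it through.** **Inputs from the Protocol.** 22 verified and one third having surgery: 22 / (1/3) = 66, as stated. On that expectation 66 − 22 = 44 patients have no surgical reference. The one third refers to surgery; intracranial EEG without resection also counts as verification, so the verified fraction may be higher. I take the 22 as given.

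**Assumptions, not in the Protocol.** True sensitivity S, true specificity P, prevalence of the target, and R = P(verified | hrMRI+) / P(verified | hrMRI−). All values below are illustrations.

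**Bias when verification depends only on hrMRI.** With a verification rate v in negatives and Rv in positives, v cancels:

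- observed sensitivity = S·R / (S·R + 1 − S)
- observed specificity = P / (P + (1 − P)·R)

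| R | S = 0.30 | S = 0.15 | P = 0.90 |
|---|---|---|---|
| 0.5 | 0.176 | 0.081 | 0.947 |
| 1 | 0.300 | 0.150 | 0.900 |
| 2 | 0.462 | 0.261 | 0.818 |
| 3 | 0.563 | 0.346 | 0.750 |

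For example, at S = 0.30 and R = 2: 0.60 / (0.60 + 0.70) = 0.462.

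**Contrast with bMRI.** Let h and b be the true sensitivities of hrMRI and bMRI, and c = 0.90 the assumed share of bMRI-positive target patients who are also hrMRI-positive. Observed bMRI sensitivity = b(cR + 1 − c) / (hR + 1 − h).

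- h = 0.15, b = 0.05 (true difference 0.10): R = 2 gives 0.261 − 0.083 = 0.178; R = 3 gives 0.346 − 0.108 = 0.238.
- h = 0.30, b = 0.10 (true difference 0.20): R = 2 gives 0.462 − 0.146 = 0.315 (from unrounded values); R = 3 gives 0.563 − 0.175 = 0.388 (likewise).

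**If the clinical report, not the study read, drives verification.** Assume prevalence 70% and both readings at 30%/90%, with the report positive in 80% of read-positive target patients and 50% of read-positive non-target patients. Agreement is 0.168 + 0.448 + 0.015 + 0.255 = 0.886. At R = 2, sensitivity is (0.168·2 + 0.042) / 0.910 = 0.415 and specificity (0.015·2 + 0.255) / 0.330 = 0.864. At R = 3 they are 0.487 and 0.833. Weighting by the report recovers 0.300/0.900. Weighting by the study read gives 0.302 with 0.912 (R = 2) or 0.917 (R = 3).

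**R = 1 is not sufficient.** Assume prevalence 70%, true 30%/90%, and one third verified in each hrMRI stratum, but with rates that depend on true status: 36% (target) and 15% (no target) in positives, 25% and 48% in negatives.

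- Sensitivity = 0.21·0.36 / (0.21·0.36 + 0.49·0.25) = 0.38.
- Specificity = 0.27·0.48 / (0.27·0.48 + 0.03·0.15) = 0.97.

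Weighting by hrMRI does not repair this. The odds of the target in unverified versus verified patients are (0.64/0.36)/(0.85/0.15) = 0.31 in positives and (0.75/0.25)/(0.52/0.48) = 2.77 in negatives. The 0.31 lies outside a range of 1/3 to 3 but inside 1/4 to 4.

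**Hypothetical data, 66 scanned and 22 verified.** hrMRI-positive: 15 scanned, 9 verified (8 TP, 1 FP). hrMRI-negative: 51 scanned, 13 verified (9 FN, 4 TN).

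- Verified-only: 8/17 = 47.1%; 4/5 = 80.0%.
- Weights 15/9 and 51/13: TP 13.33, FP 1.67, FN 35.31, TN 15.69. Corrected sensitivity 13.33/48.64 = 27.4%; specificity 15.69/17.36 = 90.4%. Bootstrap 95% intervals: 14–44% and 58–100%.
- Odds of the target in unverified patients multiplied by 1/4 to 4, independently in each stratum: 21.7–37.9% and 72.2–96.0%.

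**Behaviour of the correction.** 40,000 simulated studies per setting, 66 scanned, one third verified, true 30%/90%, R = 2 and 3. Corrected sensitivity averages 30–31% (SD 0.06–0.10) at prevalences of 60–95%. Corrected specificity:

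| Prevalence | Mean | SD | Not estimable |
|---|---|---|---|
| 60% | 89–90% | 0.09–0.10 | under 1% |
| 80% | 86–88% | 0.18–0.21 | 2–3% |
| 90% | 82–86% | 0.27–0.32 | 15–18% |
| 95% | 78–84% | 0.33–0.38 | 38–43% |

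**The case against.** The strongest reply is that dependence on hrMRI is nowhere stated. The record serves clinical care, the one surgical use the Protocol names for the images is navigation planning, and semiology, EEG and SPECT are available before the study scan. This stands as a limit on what can be claimed: R and its direction are unknown. It does not make verified-only accuracy safe, since nothing separates selection from the report.

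A second reply is that supplementary analyses belong in a SAP and that the planned counts and descriptive statistics already cover part of this. The Protocol itself, however, fixes the primary analysis set and gives unoperated patients a descriptive role. Descriptive findings supply inputs for a correction but not a corrected estimate.

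Third, the ratio of sensitivities is nearly stable: a true 3.00 becomes 3.16 at R = 2 and 3.21 at R = 3 with c = 0.90. That is correct, though a lower c would move it more, and the absolute sensitivities and specificities that form the primary outcome still shift.

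Fourth, the correction is weak for specificity when nearly all patients have the target, and it cannot repair selection on unrecorded factors. Both points stand. They argue for keeping the verified-only figures and adding a sensitivity analysis, not for omitting the correction. The study read also needs a rule for disagreement between the two radiologists.

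**Conclusion.** The concern holds as a conditional one. The structure is certain from the text: verified-only primary accuracy, about one third expected to have surgery, and a report visible to clinicians. The size is not. For R between 0.5 and 3, a true 30%/90% would be reported anywhere from 18%/95% to 56%/75%. Bias from this source is absent only if R = 1 and, given hrMRI, verification is also independent of true status. It should be addressed, with medium confidence, because the remedy is cheap and uses data the study will already hold.

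**What to change.** In the Statistical analysis protocol section:

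1. Tabulate the numbers scanned and verified by hrMRI result (positive or negative), once by the formal clinical report and once by the study read, with a stated rule for combining the two radiologists. Count both intracranial EEG and resection as verification.
2. Keep the verified-only figures. Beside them report verification-corrected sensitivity for hrMRI and bMRI, and specificity where enough verified target-negative patients exist, with bootstrap confidence intervals. Weight each verified patient by scanned/verified in the stratum of the hrMRI report that clinicians saw; this is the Begg-Greenes estimator if report and study read coincide. The same weights serve bMRI.
3. Add a sensitivity analysis for verification that depends on unrecorded factors. Within each stratum, vary the odds of the target in unverified versus verified patients, for example from 1/4 to 4, and state that range as an assumption.

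The cost is analysis work and coding each formal report as positive or negative. Intervals will be wide with about 22 verified patients, and specificity may have to be reported as not estimable. The correction in item 2 assumes that verification depends only on the recorded MRI result; item 3 is the only guard against other dependence.

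### The primary comparison is of paired readings, but the named chi-square test has no paired form, and its p-value then depends on patients positive on both scans

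*Protocol*

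**What the plan says.** Under Study protocol, the design is a "prospective cohort model comparing baseline MRI and high-resolution MRI in delineation of focal abnormalities accounting for epilepsy". Under Sample size calculation, the analysed group is approximately "22 patients who needs to have both MRI done and undergone surgery". Under Image interpretation, "The baseline MRI of the patients will be retrospectively reviewed", the study MRI is read as well, and one rule is given for a positive study: "A likelihood score of 3 or above would indicate a positive imaging study".

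The primary outcome, under Statistical analysis protocol, is the sensitivity and specificity of each scan against surgical findings. For the test, the "two tiers of MRI studies (baseline MRI and high-resolution MRI) will be compared with use of contingency table and chi-square test". The protocol names no McNemar test, matched table or other paired method, and the sample size section names no test at all.

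Two further statements bear on how many patients could be positive on both scans. Eligibility requires a "Previous MRI (at least one study with protocol tailored for epilepsy) which did not reveal accountable focal lesion". The sample size section nevertheless assumes "a 5% false negative rate on patients who actually had lesions on previous baseline MRI".

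**The concern.** Each verified patient contributes two readings, one per scan, judged against the same reference. The evidence on which scan is more sensitive comes only from reference-positive patients in whom the scans disagree. The same holds for specificity among reference-negative patients.

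Read in the ordinary way, the named test puts 22 patients read twice into a table of 44 readings and treats them as independent. Its result then depends on how many patients are positive on both scans, although they say nothing about the difference. The primary verdict could turn on them, and the direction of the error depends on a share that the protocol does not give. If the wording is meant to cover either form, the choice between two tests that can disagree stays open until the data are seen.

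**Working it through.** **Inputs from the protocol.** About 22 patients with both MRIs and surgery; two-sided alpha 0.05; score 3 or above counts as positive; assumed rates of 15% (high-resolution pick-up), 5% (false negatives) and, for the cited 7T study, 30%.

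**The plan's own figure.** 22 / (1/3) = 66 reproduces. The 22 itself does not follow from 15%, 5%, 80% power and two-sided 0.05: two independent proportions need 141 per group, and McNemar's test with 15%/5% discordant needs 155 pairs. That is a separate matter; 22 is used here only as the planned number of verified patients.

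**Assumptions, because the protocol gives no joint distribution.** For sensitivity, all 22 are reference-positive. Discordant rates and both-positive shares are illustrative.

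**Formulas.** Let a = positive on both, b = high-resolution only, c = baseline only, d = negative on both, n = a + b + c + d.

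- McNemar: X² = (b − c)² / (b + c). Neither a nor d enters.
- Pearson on the scan-by-result table, no continuity correction: X² = [(b − c)² / (b + c)] × 2n(b + c) / [(2a + b + c)(2d + b + c)].

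The denominator of the second factor equals 2n(b + c) + 4ad − (b + c)². When b and c differ, Pearson's statistic is therefore larger than McNemar's if 4ad < (b + c)² and smaller if 4ad > (b + c)².

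**One set of discordant results: n = 22, b = 6, c = 0.** McNemar: X² = 36/6 = 6.0, p = 0.014; exact p = 2 × 0.5⁶ = 0.031; mid-P = 0.031 − 0.5⁶ = 0.016. Pearson is 6 × 264 / [(2a + 6)(2d + 6)]:

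| a | d | Pearson X² | Pearson p |
|---|---|---|---|
| 0 | 16 | 6 × 264/228 = 6.95 | 0.008 |
| 1 | 15 | 6 × 264/288 = 5.50 | 0.019 |
| 2 | 14 | 6 × 264/340 = 4.66 | 0.031 |
| 4 | 12 | 6 × 264/420 = 3.77 | 0.052 |
| 8 | 8 | 6 × 264/484 = 3.27 | 0.070 |

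Pearson crosses 0.05 on the same paired evidence.

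**Small counts: n = 22, b = 4, c = 0.** With a = 0, Pearson X² = 4 × 176/160 = 4.40, p = 0.036. With a = 1, X² = 4 × 176/228 = 3.09, p = 0.079. McNemar chi-square is 0.046, mid-P 0.063 and exact 0.125 in both cases.

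**Rejection rates, exact multinomial enumeration, n = 22, two-sided 0.05.** The Pearson columns are by both-positive share.

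| Discordant b/c | Pearson 0% | 5% | 10% | 20% | McNemar chi-square | Mid-P | Exact |
|---|---|---|---|---|---|---|---|
| 15%/5% (power) | 19.2% | 11.6% | 7.4% | 3.6% | 16.6% | 9.9% | 4.4% |
| 30%/0% (power) | 93% | 81% | 70% | 56% | 93% | 84% | 69% |
| 10%/10% (type I error) | 5.6% | 2.9% | 1.6% | 0.55% | 4.7% | 2.1% | 0.6% |

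Pearson's power falls below mid-P from about 7% both-positive at 15%/5% and about 4% at 30%/0%. With 15 reference-positive patients the points are about 16% and 11%.

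**Specificity.** Assume 7 of the 22 are reference-negative and the discordant counts are 4 and 0. Pearson gives 0.018 with none positive on both and 0.031 with one or two. McNemar chi-square gives 0.046, mid-P 0.063 and exact 0.125. Here the gap comes from the large-sample approximation rather than from joint positives.

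**The case against.** **The wording may already mean McNemar.** It is a chi-square test on a contingency table, and the sample size section shows that the authors know each patient has both scans. This stands as far as it goes: the text does not exclude it. But the protocol itself fixes the primary test, and the two readings can give opposite verdicts, such as 0.052 against 0.014 in the table, so the ambiguity needs closing.

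**Joint positives may be rare.** Patients enter after a negative epilepsy-protocol MRI. With none positive on both and 15%/0% discordant, Pearson and McNemar chi-square have the same power, 42.5%. This stands for that case. At 5% both-positive, however, Pearson falls to 25.9%. The share need not be zero, because the baseline scan is re-read by radiologists who know the suspected site, and an equivocal score counts as positive.

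**The scenarios are generous or assumed.** The 5% in the protocol applies to patients with lesions on the earlier scan, so using it as a baseline-only rate among all patients is an assumption. The 30% is the 7T rate that the protocol halves. At 15%, about 3 of 22 would be positive on the high-resolution scan only, and 3 against 0 with none on both is non-significant under every test (Pearson 0.073, McNemar chi-square 0.083, mid-P 0.125, exact 0.25). All of this is fair and limits the claim on size. It does not touch the algebra: a enters Pearson's statistic and not McNemar's.

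**Mid-P is a further choice beyond pairing.** This also stands. Any McNemar version cures the pairing fault, and mid-P has less power than the chi-square version.

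**Conclusion.** The concern holds. The data are paired and the primary test is fixed without a paired form. As ordinarily read, it lets patients positive on both scans move the p-value across 0.05: from 0.008 to 0.070 in the 6-against-0 example, while each version of McNemar's test stays constant.

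The error runs in both directions. With appreciable joint positivity, Pearson loses power against mid-P. With few joint positives and small counts, it can declare significance where mid-P and exact tests do not (0.036 against 0.063 and 0.125 for 4 against 0). When joint positives are rare, Pearson and McNemar chi-square are close for sensitivity at n = 22, and the remaining issue is the large-sample approximation.

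The size rests on the assumed reference split, discordant rates and both-positive shares. The sensitivity and specificity estimates are unaffected, and a paired test does not cure the small sample. This should be fixed; confidence in its practical size is medium.

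**What to change.** In Statistical analysis protocol, replace the chi-square test with McNemar's test, mid-P version, named in advance. Apply it to the paired high-resolution-by-baseline table, within reference-positive patients for sensitivity and within reference-negative patients for specificity. Report each paired difference with a paired 95% confidence interval.

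This takes one sentence and needs no further data or patients. The cost is power when few patients are positive on both scans. At 15%/5% discordant with none on both, mid-P has 9.9% against Pearson's 19.2% at n = 22, and 3.6% against 10.0% at n = 15. The exact version has still less (4.4% and 1.0%), so it is not recommended. The McNemar chi-square version has more power (16.6% at n = 22), but its maximum type I error over equal discordant rates is 6.1%, against 5.3% for mid-P. Both slightly exceed 5%.
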